14.3 Exploratory Objectives

Associations with radial artery occlusion will be explored using a logistic regression model and adjusted for significant confounders and study cohort if the event rate for occlusion allows for a multivariable model.

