6. STUDY DESIGN

This is a prospective, randomized, single-center clinical trial.

This study will assess the outcomes of hand function utilizing the QuickDASH questionnaire, hand strength using the hand grip test, and the thumb and forefinger pinch using an electronic pinch gauge. Rates of radial artery occlusion in patients undergoing cardiac catheterization using dRA compared to pRA will be analyzed using ultrasound doppler at 1 month and 1 year.

Approximately 300 patients undergoing coronary angiography or angioplasty at The Heart Hospital Baylor Plano will be randomized 1:1 to distal or proximal radial access for cardiac catheterization.

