12.2. Potential Risks

12.2.1 Physical Risks

Possible risks include loss of sensory function in part of the hand if the cutaneous nerve running in the anatomical snuffbox becomes damaged, distal embolization can result in digital ischemia and occlusion of the branch supplying the scaphoid bone can result in bone necrosis.

A study with 656 patients reported an incidence of distal radial artery occlusion of 1.5%, haematoma of wrist and forearm (0,8%), edema (0.2%), numbress (0.6%), dissection (0.3%), arteriovenous fistula (0.2%), transient ischemic attack (0.2%), stroke (0.2%), aneurysm (0.2%), death (0.5%) (Kaledin AL, 2014;27).

A skilled and experienced operator minimizes such complications. Operators with adequate experience in distal radial access at the discretion of the Principal Investigator are eligible to participate.

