14. STATISTICAL METHODS

14. Statistical Methods

Patient demographics and characteristics will be reported and compared between the radial distal access (rDA) and proximal distal access (pDA) cohorts. Continuous variables will be reported as means ± standard deviations or medians [quartile 1, quartile 3], if skewed. Categorical variables will be reported as frequencies and percentages. Differences between demographic and clinical variables, as well as safety and compliance, will be assessed via two sample t-tests and Chi-square tests (or Wilcoxon's Rank Sum test and Fisher's Exact test), as appropriate.

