14.4 Sample Size

A Monte Carlo simulation study was utilized to study the sample size necessary to achieve at least 80% power to detect a small clinical difference between dRA and pRA in the primary composite outcome of hand function. A small clinical effect is defined as a $10\% \pm 10\%$ change in pre- to post-operation scores in at least one of the three tests for one of the study cohorts. Results from the Monte Carlo study indicate that a sample size of n=125 per group is sufficient to achieve at least 80% power under a correlation of 0.3 between the three tests. Allowing for a loss-to-follow-up rate of 15%, the total number of patients that should be enrolled for the entire study is at least 296 (148 per arm).

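### Section 14.3 picks covariates for the occlusion model by significance and fits ordinary logistic regression, although only about 4 occlusions are expected at the protocol's quoted rate

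*Combined protocol and SAP*

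**What the plan says.** Section 14.3 is one sentence. It opens "Associations with radial artery occlusion will be explored using a logistic regression model" and continues that the model will be "adjusted for significant confounders and study cohort if the event rate for occlusion allows for a multivariable model". The section is headed as exploratory. It does not list candidate covariates, define significant, name a selection test, put a number on the event-rate condition, or provide for sparse data by penalised or exact estimation.

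No expected number of occlusions is stated. The only rate is in section 12.2.1: "A study with 656 patients reported an incidence of distal radial artery occlusion of 1.5" per cent. That figure comes from an external series, and no rate is given for proximal access.

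Section 6 says that about 300 patients "will be randomized 1:1 to distal or proximal radial access for cardiac catheterization". Section 14.4 rests on 125 evaluable patients per group, and section 14.5 excludes patients lost to follow-up. Section 14.2 separately compares occlusion between the arms by a chi-square or Fisher's exact test.

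**The concern.** With very few events, keeping the covariates that reach significance does two kinds of harm. Real associations are rarely detected, and those that pass the threshold, real or not, tend to carry exaggerated estimates. Ordinary maximum likelihood is also fragile. If all the occlusions fall in one category of a covariate (separation), its estimated odds ratio is zero or infinite and the usual Wald interval is meaningless.

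The condition "if the event rate for occlusion allows for a multivariable model" is meant to guard against this. Because it has no number, the decision is left until the occlusions have been counted. If the condition stops the model, the adjusted part of the objective goes unanswered. If it does not, the selection and separation problems apply.

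At stake is whether the reported associations with occlusion can be believed, not the randomised comparison of the two access sites.

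**Working it through.** **Sample size, reproduced first.** Section 14.4: 125 / (1 − 0.15) = 147.1, rounded up to 148 per arm, and 2 × 148 = 296. This matches the plan. The planned evaluable number is 2 × 125 = 250.

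**Expected occlusions**, applying 1.5% to both arms (an assumption, since the rate is for distal access only):
- 250 × 0.015 = 3.75
- 300 × 0.015 = 4.5
- Binomial chance of 10 or more events: 0.5% (n = 250) and 1.6% (n = 300)
- Binomial chance of 3 or fewer events: 48% (n = 250) and 34% (n = 300)
- Rate needed for 15 events: 15/300 = 5%, or 15/250 = 6%. Neither rate is in the document.

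**Separation.** For a binary covariate of prevalence p that is unrelated to occlusion, all k events fall in one category with probability p^k + (1 − p)^k. With k = 4:
- p = 0.10: 0.6561 + 0.0001 = 66%
- p = 0.20: 0.4096 + 0.0016 = 41%
- p = 0.50: 0.0625 + 0.0625 = 12.5%

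The last line also applies to study cohort itself under 1:1 allocation and equal rates. With k = 15, the figure at p = 0.10 falls to 21%.

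**Chance selection.** The plan gives neither the number of candidates m nor the level. At 0.05 with independent tests of exact size, P(at least one selected) = 1 − 0.95^m:
- m = 3: 14%
- m = 5: 23%
- m = 8: 34%
- m = 10: 40%
- m = 12: 46%

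Tests are not of exact size with so few events, so the case of 10 candidates was simulated. The set-up was 250 patients, 8 binary covariates of prevalence 15% to 75%, 2 continuous covariates, all unrelated to occlusion, and 4,000 replicates. For the Fisher and chi-square rows, the continuous covariates were tested by likelihood ratio.

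| Screening test | At least one selected: 4 events | 5 to 15 events | Selected with OR >10, <0.1, zero or infinite: 4 events | 5 to 15 events |
|---|---|---|---|---|
| Fisher | 23% | 24–31% | 12% | 3–8% |
| Chi-square | 36% | 35–38% | 16% | 5–11% |
| Likelihood ratio | 38% | 44–50% | 24% | 13–32% |
| Wald | 15% | 18–28% | 5% | 0.2–4% |

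So the chance of at least one spurious covariate is roughly 20% to 50%, falling to 15% with a Wald screen at 4 events. The chance that a selected covariate also has an extreme odds ratio is lower in every row.

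**The case against.** The strongest defence is that the sentence already contains a safeguard. At about 4 events a sensible analyst would not fit a multivariable model, so the worst case may never arise, and the simulation above does not apply that condition. The occlusion comparison in section 14.2 is unaffected, and the analysis is labelled exploratory. This largely stands and is why the point is minor. It does not remove the point, because a condition without a number can be settled either way once the counts are known.

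A second objection is that ten candidates, the 0.05 level and the test are all assumed. That also stands. With 3 candidates the formula gives 14%, so the percentages illustrate the risk and are not predictions.

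A third concerns confounding. Randomisation means that baseline factors do not systematically confound the cohort effect. However, section 14.3 is about associations with occlusion, and those of non-randomised patient or procedural factors can be confounded. Adjustment as such is therefore reasonable; selecting the adjusters by significance is the weakness.

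A reader might infer that more than 40% of trials would report a chance association with a very large or infinite odds ratio. The documents do not support this. Forty per cent is the formula's chance of any false-positive covariate among ten assumed candidates. Selection together with an odds ratio above 10, below 0.1, zero or infinite occurred in 0.2% to 32% of simulated trials over 4 to 15 events. A separate simulation with 300 patients and a likelihood-ratio screen puts selection together with separation at 0.435 × 0.775 = 34%, 0.461 × 0.478 = 22% and 0.437 × 0.188 = 8% for occlusion rates of 1.5%, 3% and 5%. A reader might also take 5 to 15 as the plan's expected event range, but the one quoted rate gives about 4.

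**Conclusion.** The concern holds in limited form. Section 14.3 selects covariates by significance and fits ordinary logistic regression where about 4 events are expected (3.8 of 250 or 4.5 of 300). At that count separation is common: 66% to 13% of trials for a single unrelated binary covariate of 10% to 50% prevalence. Screening about 10 candidates would select at least one by chance in roughly 20% to 50% of trials.

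These figures assume the 1.5% rate in both arms, 10 independent candidates, a two-sided 0.05 level and the stated prevalences. A higher occlusion rate would ease separation but would not justify choosing covariates by significance. Severity is minor: the analysis is exploratory and carries no confirmatory claim.

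**What to change.** Replace the sentence in section 14.3 with wording such as:

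*Associations with radial artery occlusion will be estimated by Firth penalised logistic regression with profile-likelihood intervals. The covariates are study cohort and a short list fixed in advance from data already recorded (for example diabetes and sheath size). No covariate will be selected by significance. The number of covariates fitted together will follow a rule based on the pooled number of occlusions, set before any unblinded analysis. With fewer than [number] events, only one-variable-at-a-time Firth or exact estimates will be given; with no events, no model will be fitted. Results are exploratory.*

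The sponsor should fill in the number and the list now. The pooled rule matters: cohort plus two covariates is three slopes, and 3 or fewer events would occur in 34% to 48% of trials at 1.5%, so fitting that model whatever the count would be unsound. If sheath size is listed, confirm that it is recorded in both arms, since section 9.3 mentions it only for distal access. It is also a procedural factor fixed after allocation, so the cohort coefficient adjusted for it should not be read as the randomised effect.

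The cost is a few lines of SAP text and a standard software option. The downside is fewer covariates and wide intervals, which show how little information there is.

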14.4 Sample Size

A Monte Carlo simulation study was utilized to study the sample size necessary to achieve at least 80% power to detect a small clinical difference between dRA and pRA in the primary composite outcome of hand function. A small clinical effect is defined as a $10\% \pm 10\%$ change in pre- to post-operation scores in at least one of the three tests for one of the study cohorts. Results from the Monte Carlo study indicate that a sample size of n=125 per group is sufficient to achieve at least 80% power under a correlation of 0.3 between the three tests. Allowing for a loss-to-follow-up rate of 15%, the total number of patients that should be enrolled for the entire study is at least 296 (148 per arm).

14.5 Loss to Follow-up

Subjects lost to follow-up will be excluded from the analyses. Demographics and baseline characteristics will be compared between included and lost-to-follow-up subjects.

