12.2.3 Adverse Event Reporting

An Adverse Event (AE) is any untoward sign, symptom or medical condition occurring at any time after the subject receives his/her procedure, even if the event is not considered to be related to the study. Abnormal laboratory values or test results constitute AEs only if they induce clinical signs or symptoms, are considered clinically significant, or require therapy.

The adverse events that will be monitored and reported from the start of the study procedure until 1 year after the index procedure are complications related to the procedure which include:

- Bleeding
- Hematoma
- Radial Occlusion

A Serious Adverse Event (SAE) is an undesirable sign, symptom or medical condition which:

- is fatal
- is life threatening
- requires or prolongs hospitalization
- results in persistent or significant disability/incapacity
- constitutes a congenital anomaly or a birth defect
- is medically significant, in that it may jeopardize the subject and may require medical or surgical intervention to prevent 1 of the outcomes listed above
- Hospitalizations not necessarily considered to be SAEs are hospitalizations for:
- treatment, which was elective or preplanned, for a pre-existing condition that is unrelated to the indication under study and did not worsen
- treatment on an emergency, outpatient basis for an event not fulfilling any of the definitions of serious given above and not resulting in hospital admission

All SAEs will be followed up until resolution or permanent outcome of the event.

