14.1 Analysis of Primary Composite Outcome

The primary composite outcome of hand function will be defined utilizing the average Z-score approach (O'Brien, 1984; Sun, 2012). The average z-score for each subject is calculated as the average of the z-scores of the differences between pre- and 1-month post-operation measurements for three individual tests. The three tests that measure everyday functionality and strength of a subject's hand included in the composite outcome are: (a) the QuickDASH questionnaire score (0-100) calculated as [(sum of n responses / n) – 1] * 25, (b) Thumb and forefinger pinch strength test (kg), and (c) hand grip strength test (kg). The average of the three z-scores are then compared between rDA and pDA using the Wilcoxon rank-sum test.

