14.2 Analysis of Secondary Outcomes

The composite outcome of hand function will be compared at 12-months post-operation using the average z-score approach outlined in the primary outcome analysis. The success rate, hematoma, bleeding, and radial artery occlusion will be compared between rDA and pDA cohorts using a Chi-square test (or Fisher's exact test). The rate of complications (including occurrence of hematoma, bleeding, radial artery occlusion, and complications of vascular access) per subject will be compared between the study cohorts using a Poisson Exact test.

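### Section 14.5 drops lost subjects from every analysis, without limit by endpoint or visit, and so can discard outcomes already observed

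*Combined protocol and SAP*

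**What the plan says.** Section 14.5 has two sentences. The first is the rule: "Subjects lost to follow-up will be excluded from the analyses". The second is the only accompanying check: "Demographics and baseline characteristics will be compared between included and lost-to-follow-up subjects". Together they sort subjects once, into included or lost. Loss to follow-up is not defined anywhere, and no section sets out an analysis population or says what happens to data collected before loss.

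The endpoints to which the rule would apply become known at different times:

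- **Primary composite (14.1):** built from "differences between pre- and 1-month post-operation measurements for three individual tests".
- **Secondary composite (14.2):** "The composite outcome of hand function will be compared at 12-months post-operation".
- **Procedural and safety outcomes (14.2):** "The success rate, hematoma, bleeding, and radial artery occlusion will be compared between rDA and pDA cohorts". The complication rate "per subject will be compared between the study cohorts using a Poisson Exact test".
- **Adverse events (12.2.3):** bleeding, hematoma and radial occlusion are "monitored and reported from the start of the study procedure until 1 year after the index procedure".
- **Radial artery occlusion (Section 6):** rates "will be analyzed using ultrasound doppler at 1 month and 1 year".

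Section 14.4 allows for 15% loss without saying by which visit.

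**The concern.** One subject-level status cannot serve endpoints observed at the procedure, during the following year, at month 1 and at month 12. Taken literally, the rule has three effects:

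1. Access success is settled on the day of the procedure but is dropped because of a visit missed later.
2. Bleeding or hematoma recorded before loss disappears from the between-arm tests.
3. A subject who attends month 1 and misses month 12 can lose a complete primary record.

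If loss is unrelated to outcome, the price is precision only. If loss depends on outcome differently by arm, an event after randomisation decides who is analysed and the comparison is biased. Comparing baseline characteristics cannot show loss driven by a failed access or a hematoma, because neither is a baseline variable. The wording also leaves two possible denominators for each test, and the choice between them could be made after results are seen.

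**Working it through.** **Inputs from the documents.** 125 evaluable per arm, power of at least 80%, 15% loss, 296 enrolled or 148 per arm (14.4); approximately 300 randomised 1:1 (Section 6); visits at 1 and 12 months (9.4); hematoma 0.8% in one cited study (12.2.1).

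**The plan's own figure.** 125 / (1 − 0.15) = 147.06, rounded up to 148 per arm; 2 × 148 = 296. This reproduces. The simulation behind 125 cannot be rerun, because alpha and the effect on the z-score scale are not given. Nothing below depends on rerunning it.

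**Subjects dropped from access success.** 0.15 × 296 = 44.4 (0.15 × 300 = 45). Standard errors are multiplied by 1/√0.85 = 1.085.

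**Power for access success (assumed rates, loss unrelated to outcome).** Exact enumeration of the uncorrected two-sided 5% chi-square test:

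| Assumed success rates | 148 per arm | 126 per arm |
|---|---|---|
| 90% vs 97% | 70.3% | 63.3% |
| 85% vs 95% | 83.8% | 77.7% |
| 95% vs 97% | 13% | 11% |

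**Recorded events discarded (loss unrelated to events, the same rate applied to both arms).**

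- At 0.8%: 44.4 × 0.008 = 0.36 of 296 × 0.008 = 2.37 expected hematomas.
- At an assumed 5%: 44.4 × 0.05 = 2.2 of 296 × 0.05 = 14.8.

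**Complete 1-month records discarded.** Take 300 enrolled and 15% lost by month 12. The share already lost by month 1 is an assumption:

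- 5% by month 1: 300 × (0.15 − 0.05) = 30 records discarded
- 10%: 300 × 0.05 = 15
- 15%: none

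**Primary power.** With 15% lost in total, 148 × 0.85 = 125.8 per arm, which meets 125. Now suppose a further share x of those seen at month 1 miss only month 12 and are excluded as well. Then n = 125.8 × (1 − x), and power = Φ((1.96 + z) × √(n/125) − 1.96), where z is the normal quantile of the power at 125 per arm.

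| x (assumed) | n per arm | Power if 80% at 125 | Power if 90% at 125 |
|---|---|---|---|
| 0 | 125.8 | 80.2% | 90.2% |
| 5% | 119.5 | 78.2% | 88.7% |
| 10% | 113.2 | 76.0% | 87.0% |

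The 90% column is shown because the plan promises at least 80%.

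**Does keeping events recorded before loss create its own distortion?** Assume no true difference, unrelated loss at month 1 of 15% in one arm and 5% in the other, and a share f of events after month 1. The per-subject rate ratio is (1 − 0.15f)/(1 − 0.05f):

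- f = 0: 1.00
- f = 0.1: 0.985/0.995 = 0.99
- f = 0.3: 0.955/0.985 = 0.97

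The distortion is small when loss is unrelated to outcome. This does not test outcome-related loss.

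**The case against.** The strongest reply is that this is loose wording and not a harmful rule. Section 14.5 directly follows the sample-size section, where loss to follow-up concerns only the primary composite. A subject without 1-month tests has no 1-month difference to analyse, so the sentence may simply restate complete-case analysis. The single split into included and lost fits one primary analysis set and does not prove that access success would be dropped. That reading is possible, but the plan does not state it, and the literal reading gives different denominators.

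Several points about size stand:

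- The 15% may already mean loss through month 12. In that case even literal exclusion leaves enough subjects for the primary.
- The further 5% or 10% loss is hypothetical. With 300 enrolled in place of 296, about 121 or 115 per arm remain and power is 78.8% or 76.6% (if 80% at 125), under one point from the figures above.
- The access-success rates are assumed, the trial is not powered for that endpoint, and at 95% vs 97% the loss of power is immaterial.
- At the one hematoma rate in the documents, almost no events are lost.
- Section 12.2.3 still requires events to be monitored and reported, so only the between-arm tests are affected.
- No passage gives a mechanism or direction for outcome-related loss.

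These points limit the size of the effect. They do not supply the missing limit by endpoint and visit.

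**Conclusion.** The concern holds. The rule excludes whole subjects, nothing in the documents narrows it, and followed as written it discards observed outcomes.

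The firm part, at the planned 15% loss, is about 44 of 296 subjects removed from access success and standard errors about 8.5% larger. The cost in primary power is nil at 15% total loss. It becomes a few points only if further subjects who miss just month 12 are excluded. The loss of recorded hematomas is small at 0.8%, and larger only if rates are higher or loss is related to events. The bias is a possibility that the documents neither support nor rule out.

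The sponsor should make this change. Confidence is medium, because the consequence depends on how the sentence would be applied.

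**What to change.** Define loss separately for each visit and replace 14.5 with an observed-data rule per endpoint:

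- **Access success:** all randomised subjects who had the procedure, in their assigned arm, whatever their later follow-up.
- **Bleeding, hematoma and the per-subject complication comparison:** the same set, keeping every event recorded before loss and keeping the planned per-subject rate. Because events after loss are unseen, report by arm the number and timing of losses and the number without a Doppler at each visit.
- **Radial artery occlusion:** all subjects with a Doppler at the visit concerned, with separate denominators for 1 and 12 months.
- **Primary composite:** all subjects with 1-month tests, whether or not the 12-month visit took place.
- **12-month composite:** all subjects with 12-month tests.

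Optionally, add one sensitivity analysis of the composite that multiply imputes the three test scores from arm, baseline scores and observed procedural outcomes.

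The cost is SAP wording, an amendment submitted to the IRB under Section 15.1, and a little extra analysis and reporting. No new data are needed and the enrolment target is unchanged. These rules cannot recover events that occur after loss, and they do not remove bias if loss is related to outcome. If the sponsor always meant the narrower reading, the new wording simply records it.
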